6.5. Baseline and Other Summaries and Analyses

6.5.1. Baseline Summaries

Baseline characteristics presented in Section 3.4 will be summarized using descriptive statistics.

6.5.2. Study Conduct and Participant Disposition

An accounting of the study patients will be tabulated including enrolled, evaluable for PRO, and safety (treated). Patients not meeting the eligibility criteria will be identified. Patients not completing the study will be listed along with the reason for their premature discontinuation.

Reasons for premature discontinuation will be summarized. Unexpected treatment (e.g., palbociclib therapy in Group 2) will be described.

6.5.3. Study Treatment Exposure

The extent of treatment will be summarized as follows:

- Number of cycles started
- Duration of a cycle (weeks)

For Group 1 (palbociclib plus endocrine therapy)

- Starting dose: 125 mg, 100 mg, 75 mg
- Number of patients with no dose reduction, at least 1 dose reduction, 2 dose reductions
- Patients with cycle delay

6.5.4. Concomitant Medications and Nondrug Treatments

Radiation treatment and general surgery during the observation period and follow-up cancer therapy will be listed and summarized.

6.6. Safety Summaries and Analyses

Overall safety profile as characterized by type, frequency, severity of adverse events as graded by NCI Common Toxicity Criteria for Adverse Events version 4 (NCI CTCAE v.4.0), timing and relationship to treatment.

Adverse events will be classified using the MedDRA classification system. The severity of the toxicities will be graded according to the NCI CTCAE version 4. For other AEs without specific CTCAE definitions, results are identified according to CTCAE “other” categories.

Adverse events leading to death or discontinuation of study treatment, events classified as NCI CTCAE v.4.0 Grade 3 or higher, treatment-related events, study procedure-related events and serious adverse events will be considered with special attention.

Patients who start treatment are assessed for toxicities up to 28 days after the final dose of treatment or start of new treatment (whichever comes first). Toxicities observed beyond 28 days and recorded in the database per Sponsor’s agreement will be included in the summaries.

Frequency distributions of the worst grade of the adverse events will be summarized for all-causality and treatment-related adverse events, respectively. Grade 3 or higher events, serious adverse events, discontinuations due to adverse events will be summarized separately for all-causality and treatment-related adverse events. All adverse events including deaths and serious adverse events will be listed.

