9. RESEARCH METHODS

9.1. Study design

The study is a prospective, multicenter, observational study to evaluate PRO and physical activity using smartphone-based application and wearable device in Japanese patients with HR+/HER2- ABC.

Patients will be enrolled into either palbociclib plus endocrine therapy group (Group 1) or endocrine monotherapy group (Group 2) based on the discretion of the treating physician under routine clinical practice. Total target number of patients is approximately one-hundred in this study (assuming about 20 to 80 patients in each group). The number of enrolled patients will be monitored, and the enrollment will be completed when 100 patients have been enrolled. Of note, the patient who is informed about this study for participation at the time when the number of enrolled patients reaches 100 is allowed to enroll. Enrolled patients will download a smartphone-based application for electronic PRO (ePRO), be provided access to and trained on the use of the application to complete baseline, weekly, and cycle-based assessments for 6 cycles (24 weeks). In addition, enrolled patients will be provided with wearable device and requested to wear the device at all-times, except of while bathing and sleeping, for 6 cycles (24 weeks).

[figure not shown]
In this study, one cycle is defined as follows;

- In Group 1 (palbociclib plus endocrine therapy), palbociclib is administered for 3 consecutive weeks followed by 1 week off treatment to comprise one cycle of 4 weeks. If palbociclib is temporarily interrupted (eg, due to adverse event) and the start of the next cycle is delayed, the duration of one cycle may exceed 4 weeks, then, the observation period may exceed 24 weeks.
- In Group 2 (endocrine monotherapy), one cycle is defined as 4 weeks.

Participation in this study is not intended to change the routine treatment that patients receive as determined by their prescribing clinicians; all treatment decisions and type and timing of disease monitoring are at the discretion of the treating physician. No additional visits to the clinic will be required for the purposes of the study.

Figure 1 summarizes the overall study design.

Figure 1. Study Design

It is anticipated that all data collection for this study will occur over a 24-month period (from the first patient's first visit to the last patient's end of study assessment),

Planned patient enrollment duration: 18 months

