12.5. Data analysis

For the purpose of this study, analyses will generally be descriptive in nature and will be conducted. All analysis will be summarized separately by groups except for the between group comparison. Detailed methodology for summary and statistical analyses of data collected in this study will be documented in a SAP, which will be dated, filed and maintained by JBCRG and Pfizer. The SAP may modify the plans outlined in the protocol; any major modifications of primary endpoint definitions or their analyses would be reflected in a protocol amendment.

All variables will be summarized descriptively through tabular displays of mean, median, ranges and standard deviations of continuous variables and frequency distributions of categorical variables by measured points.

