16.1. Adverse Events (AE)

An AE is defined as any untoward medical occurrence and can therefore be any unfavorable and unintended sign (including an abnormal laboratory finding), symptom, or disease, whether or not related to the subject's participation in the study.

AE reporting period for each subject begins from the time the subject provides informed consent, through the end of the observation period of the study which must include at least 28 calendar days following the last administration of the drug under study. **Any AE related to**

PFIZER CONFIDENTIAL

above procedure that occurs from the time the subject consents to the clinical research through and including 12 hours after completion of the qualifying procedure must be recorded. The investigator is required to assess whether the AE may be related to the subject's participation in the study. All AEs (ie, serious and non-serious, including those attributed to qualifying procedure identified as research-related injury) are collected in the clinical study database.

The investigator must pursue and obtain information adequate to determine the outcome of the AE and to assess whether it meets the criteria for classification as a research-related injury requiring immediate notification to Pfizer as described below.

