16.2.4. Time Period for Collecting AE/SAE Information

The time period for actively eliciting and collecting AEs and SAEs (“active collection period”) for each subject begins from the time the subject provides informed consent, which is obtained before the subject’s participation in the study (ie, before undergoing any study-related procedure and/or receiving the marketed product under study), through the end of the

observation period of the study which must include at least 28 calendar days following the last administration of the drug under study.

For subjects who are screen failures, the active collection period ends when screen failure status is determined.

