4. ANALYSIS SETS (POPULATIONS FOR ANALYSIS)

Data for all participants will be assessed to determine if participants meet the criteria for inclusion in each analysis population prior to releasing the database and classifications will be documented per standard operating procedures.

Population	Description
Enrolled	All participants who sign the informed consent document.
Evaluable	All participants who enrolled in the study and who respond at least 1 item or measured at least 1 metrics of study application or device. Participants will be analyzed according to the enrolled group.
Safety	All participants who receive at least 1 dose of palbociclib or endocrine therapy. Participants will be analyzed according to the enrolled group. An enrolled but not treated participant will be excluded from the safety analyses.

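### SAP 6.6 reports crude adverse event frequencies over observation windows that differ between patients and can differ between groups, with no time-at-risk denominator

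*SAP*

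**What the plan says.** **Length of the window.** Protocol 16.1 and 16.2.4 start adverse event collection at consent and run it "through the end of the observation period of the study which must include at least 28 calendar days following the last administration" (that is, of study treatment). Protocol 9.1 sets the observation period at six cycles. If the next palbociclib cycle is delayed in Group 1, "the duration of one cycle may exceed 4 weeks, then, the observation period may exceed 24 weeks", and no upper limit is given. For the other group: "In Group 2 (endocrine monotherapy), one cycle is defined as 4 weeks".

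**Closure at a new therapy.** Protocol 16.2.4.2 ends recording of non-serious events when a new anticancer therapy starts, but keeps serious events and device-related injury open for the rest of the active collection period. Protocol 16.2.4.1 likewise keeps serious event reporting open. SAP 6.6 assesses toxicities "up to 28 days after the final dose of treatment or start of new treatment (whichever comes first"), with no exception for serious events. It also admits later toxicities if they are recorded with the sponsor's agreement.

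**Analysis.** The safety set is "All participants who receive at least 1 dose of palbociclib or endocrine therapy. Participants will be analyzed according to the enrolled group". For the event tables, SAP 6.6 plans the following: "Frequency distributions of the worst grade of the adverse events will be summarized for all-causality and treatment-related adverse events, respectively". It adds separate summaries of serious events, Grade 3 or higher events and discontinuations. SAP 6.5.3 tabulates cycles started, cycle duration and patients with cycle delay, but does not connect these to the event tables. Protocol 8.2 lists the incidence of adverse events among the secondary endpoints.

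**The concern.** An incidence proportion needs a stated period. Here the period depends on what happens to the patient. In Group 1, a patient whose cycles are delayed, for example by toxicity, is watched for longer and has more opportunity to record an event or a worse grade. In either group, a patient who switches early stops contributing non-serious events but still counts as a whole patient in the denominator.

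So the crude percentage is not a 24-week incidence for either group, even when each column is read alone. If the two columns are read together, part of any difference may reflect length of observation and not toxicity.

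**Working it through.** **What the plan's figures give.** Six cycles of 4 weeks is 24 weeks (168 days), which agrees with the stated observation period. There is no exposure or event-rate figure to reproduce.

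**Delay alone.** With a constant event rate and a total delay of d weeks, the share of a delayed Group 1 patient's events that falls after week 24 is d/(24+d): 4% for d = 1, 7.7% for 2, 11.1% for 3, 14.3% for 4 and 20% for 6. The values of d are assumed. The documents say only that cycle delays were higher in Japanese patients than overall (Protocol 7). For an event with a true 24-week incidence of 40% and no switching at all, 3 extra weeks move the crude figure to 1 − 0.6^(27/24) = 43.7%.

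**Delay and switching together (illustration only).** Assumptions:
- Time to switch is exponential, with the median PFS values quoted in Protocol 7 as a proxy: λ = ln 2/median, at 4.348 weeks per month.
- The event hazard is the same in both groups: h = −ln(0.60)/24 = 0.02128 per week.
- T = 24 weeks in Group 2, and 24 or 27 weeks in Group 1 (0 or 3 weeks' delay in every Group 1 patient).
- The 28-day tail after last dose is ignored.

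Formulas: mean weeks at risk = (1 − exp(−λT))/λ; crude incidence = h/(h+λ) × (1 − exp(−(h+λ)T)).

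Worked case, overall later-line trial with a 3-week delay:
- Group 1: λ = 0.01733, so 0.5512 × (1 − exp(−0.03861 × 27)) = 35.7%.
- Group 2: λ = 0.04195, so 0.3366 × (1 − exp(−0.06323 × 24)) = 26.3%.

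All pairs are Group 1 vs Group 2; gaps come from unrounded values.

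| Source of medians (months) | Mean weeks at risk, no delay | Crude %, no delay (gap) | Crude %, 3-week delay (gap) |
|---|---|---|---|
| First-line trial, Japanese (22.2 vs 13.8) | 22.1 vs 21.0 | 37.0 vs 35.3 (1.7) | 40.1 vs 35.3 (4.8) |
| Later-line trial, Japanese (13.6 vs 11.2) | 20.9 vs 20.3 | 35.3 vs 34.4 (0.9) | 38.0 vs 34.4 (3.7) |
| First-line trial, overall (24.8 vs 14.5) | 22.2 vs 21.1 | 37.3 vs 35.6 (1.8) | 40.5 vs 35.6 (4.9) |
| Later-line trial, overall (9.2 vs 3.8) | 19.6 vs 15.1 | 33.3 vs 26.3 (7.0) | 35.7 vs 26.3 (9.4) |

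**Direction.** The Japanese hazard ratio intervals are 0.26 to 1.34 (first line) and 0.32 to 2.11 (later line). At 2.11, applied to the Group 2 median of 11.2 months, the crude figures are 29.4% vs 34.4% with no delay and 31.1% vs 34.4% with 3 weeks' delay. The sign reverses.

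**Which summaries remove the gap.** Take the overall later-line case with delay, where the gap is 9.4 points.
- Cutting at Day 168 returns Group 1 to 33.3%, which removes the delay part and leaves 7.0 points from switching.
- A 24-week cumulative incidence with switching as a competing event is the same formula at T = 24, so it also gives 33.3% vs 26.3%.
- First events per unit of time at risk: mean time to first event or closure is (1 − exp(−(h+λ)T))/(h+λ) = 16.77 vs 12.35 weeks. The rate per 28 patient-days is 4 × 0.3569/16.77 = 0.085 vs 4 × 0.2628/12.35 = 0.085. Equal hazards give equal rates.

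**The case against.** The study is descriptive and is not designed for hypothesis testing (Protocol 12.1). No decision on safety rests on a test (SAP 5.1), and comparing groups is not a primary objective. Crude incidence on treatment is a legitimate descriptive measure. SAP 6.5.3 gives some exposure context, and SAP 6.6 mentions timing and lists all events. With 20 to 80 patients per group (Protocol 9.1), sampling error around 40% is 1.96 × √(0.4 × 0.6/n), or about 21 points at n = 20 and 11 at n = 80, which is larger than any gap above. All of this stands and limits the impact. It does not supply a denominator for the stated incidence endpoint.

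A reader might infer four stronger claims that the documents do not support:
- **That the window closes at a switch for every event.** Protocol 16.2.4.1 and 16.2.4.2 keep serious events open. SAP 6.6 has no such exception, so for serious events the switch argument depends on how the passages are reconciled. The delay argument applies to them either way.
- **That switching comes sooner in Group 2, so Group 1 always looks worse.** This is inferred from randomised trials. Here the physician chooses the group, both Japanese hazard ratio intervals include 1, and Group 1 patients may also switch for toxicity.
- **That a between-group comparison of harms is planned.** Protocol 12.5 says "All analysis will be summarized separately by groups except for the between group comparison", but does not tie that comparison to safety, and no such test appears in the visible text.
- **That the extra Group 1 weeks are extra palbociclib exposure.** They arise from interruption and are calendar time at risk.

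**Conclusion.** The point holds as a gap in the safety summaries. Windows are unequal by design, through delay in Group 1 and through closure at a new therapy for non-serious events. SAP 6.6 plans frequencies without a time-at-risk denominator or a common cut-off. This part needs no model.

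The size cannot be fixed from the documents. The illustrative gap runs from 0.9 points to 9.4 points. The upper end needs both the overall later-line medians and a 3-week delay in every Group 1 patient, and the direction could reverse. These figures rest on exponential switching, PFS as a stand-in for switching, a constant and equal hazard, and assumed delays. Given the descriptive purpose, this is a modest but worthwhile correction.

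**What to change.** In SAP 6.6, keep the crude tables and full listings, and make these changes:

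1. By group, add total patient-time at risk and exposure-adjusted rates (events, and patients with a first event, per 28 patient-days) for all-causality, Grade 3 or higher, serious and selected events.
2. Also show the frequencies restricted to events through Day 168, with later events presented separately. This deals with delay; the rates in item 1 deal with switching.
3. State one time-at-risk definition for non-serious events and one for serious events, including how the 28-day tail and late toxicities are counted. Reconcile SAP 6.6 with Protocol 16.2.4.1 and 16.2.4.2 on serious events after a new therapy.

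A competing-risk cumulative incidence is not needed: it reproduces the switching gap and is heavy for a group of about 20 patients.

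The cost is SAP wording and a few table columns. Adverse events, treatment duration and cycle duration are already collected. The rates assume a roughly constant hazard, so they should be read beside the crude figures.

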7. INTERIM ANALYSES

Not applicable (No interim analysis is planned during study period)

8. REFERENCES

Not Applicable

9. APPENDICES

Appendix 1. Summary of Efficacy Analyses

Not Applicable

Appendix 2. List of Abbreviations

Abbreviation	Term
1L	First-Line
2L	Second-Line
95% CI	95% Confidence Interval
ABC	Advanced Breast Cancer
AE(s)	Adverse Event(s)
BMI	Body Mass Index
CDK4/6	Cyclin-Dependent Kinases 4 and 6
CTCAE	Common Terminology Criteria for Adverse Events
CM	Centimeter
ECOG	Eastern Cooperative Oncology Group
eCRF	electronic case report form
EORTC-QLQ-BR23	European Organization for Research and Treatment of Cancer Quality of Life Questionnaire-Breast23
EORTC-QLQ-C30	European Organization for Research and Treatment of Cancer Quality of Life Questionnaire for Cancer Patients30
ePRO	electronic Patient-Reported Outcome
ER	Estrogen Receptor
FACT-B	Functional Assessment of Cancer Therapy-Breast
HER2	Human Epidermal Growth Factor Receptor-2
HR	Hormone Receptor
HRQOL	Health Related Quality of Life
KG	Kilogram
MedDRA	Medical Dictionary for Regulatory Activities
MVPA	Moderate-to-Vigorous Physical Activity
NCI	National Cancer Institute
PFS	Progression-Free Survival
PRO	Patient-Reported Outcome
PRO-CTCAE	Patient-Reported Outcome - Common Terminology Criteria for Adverse Events
QOL	Quality of Life
SAP	Statistical Analysis Plan

Abbreviation	Term
TTD	Time to Deterioration
WHO	World Health Organization
